7.3 Tertiary Outcomes

In all tertiary objectives, we will check the mean change in the blood counts from Visit 1 to Visit 4 with 95% Confidence Interval by using two independent samples T-Statistics or Non-Parametric test Mann-Whitney U.

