6.1 Populations

Intention-to-treat (ITT)

All randomised study subjects. This will be seen as the primary population for the analysis.

Per Protocol (PP)

All randomised study subjects completing the whole study period (complete cases). For a specific analysis, study subjects with missing data on any of the variables in the model will be excluded from the analysis. Analyses of this population is seen as a sensitivity analysis to investigate whether conclusions are sensitive to assumptions regarding the pattern of missing data.

6.2 Groups:

Patients with with vitamin-D deficiency are divided into two groups i.e placebo group and vitamin-D group.

Placebo group: out of total 95 participants 47 participants were on placebo arm

Vitamin-D group:

Similar out of total 95 participants 48 participants were on vitamin-D arm

Vitamin-D deficiency:

All randomized study subjects will be divided into two subgroups according to having vitamin-D deficiency at baseline visit.

Division of groups:

All randomised study subjects will be divided into two subgroups according to treatment.

7. Analyses

All outcomes will be presented using descriptive statistics. As the sample size is low so we will check the normality of each variable on screening (Visit 1) and according to the normality check we will determine the mean difference change in Placebo and active treatment arm.

In descriptive analysis we will mention the mean value of each variable with lower and upper bound with 95% confidence interval, 5% trimmed mean, median, Std. Deviation as per the each group ; normally distributed data by the Mean, Variance, Standard deviation (SD), lower and upper values of the variables to see the outliers if any.

In analytical analysis we will apply T-Test for two independent samples to see the difference between two arms. In case any variable doesn't follow the normality assumptions, we will use non-parametric test.

For the safety objective we will use only frequency/number of events to present it.

SPSS 21 will be used for all statistical analysis.

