7.1 Primary outcome

The primary outcome analysis will be performed to check the difference change in Placebo group and Active Treatment group (Vitamin-D Group) through comparing mean difference from Visit 1 to Visit 4. This test will identify the mean increase or decrease in the Vitamin-D levels in the study Participants.

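### Where the SAP replaces the t-test with a rank test, it names no between-arm estimate with a confidence interval to go with the p-value

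*SAP*

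**What the plan says.** SAP 7.3 (tertiary outcomes) names the quantity of interest: "we will check the mean change in the blood counts from Visit 1 to Visit 4". It is to come with a "95% Confidence Interval by using two independent samples T-Statistics or Non-Parametric test Mann-Whitney U".

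SAP 7 sets the general rules:

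- The descriptive part lists the "mean value of each variable with lower and upper bound with 95% confidence interval", followed by "5% trimmed mean, median, Std. Deviation as per the each group". These are summaries within each arm.
- For the comparison, "we will apply T-Test for two independent samples to see the difference between two arms".
- For any variable that does not meet the normality assumption, "we will use non-parametric test". The rule covers all variables, names no particular test and attaches no estimate. Normality is judged at Visit 1.

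SAP 7.1 analyses the primary outcome "through comparing mean difference from Visit 1 to Visit 4", and 7.2 does the same for the secondary outcomes. Neither states a confidence interval.

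Protocol 7 names a Wilcoxon test without an estimate, a baseline-adjusted linear regression for continuous outcomes, and a risk ratio with a 95% CI for categorical outcomes. The SAP carries over neither of the two models.

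**The concern.** Mann-Whitney U ranks the pooled observations. It does not estimate a mean or a difference in means, so the sentence in 7.3 asks for something that one of its two methods cannot supply. An analyst who follows it for a skewed count has two choices: print a t-based interval for the mean change next to the rank p-value, or print the p-value without an interval. The general switching rule in SAP 7 creates the same choice for 25(OH)D, CD4 count, viral load and liver enzymes.

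In the first case the reader sees an interval and a p-value that answer different questions and may point in different directions. In the second, the precision of the treatment effect is not reported. The primary objective asks whether the dose is sufficient, so the size of the effect and its uncertainty matter more than a significance verdict.

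**Working it through.** The plan gives no figure on this point to reproduce, and its sample-size calculation plays no part in it. The check is a comparison of the sections, followed by a simulation.

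**1. What each section supplies**

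| Place | Quantity | Test | Between-arm 95% CI | Estimate tied to the rank test |
|---|---|---|---|---|
| SAP 7 | per-arm mean, trimmed mean, median | t, or an unnamed non-parametric test | none stated | none |
| SAP 7.1, 7.2 | difference in mean change, Visit 1 to 4 | by the rule in SAP 7 | none stated | none |
| SAP 7.3 | mean change, Visit 1 to 4 | t or Mann-Whitney U | implied with t; not obtainable from U | none |
| Protocol 7 | baseline-adjusted regression; risk ratio | regression; Wilcoxon | risk ratio only | none |

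**2. What the rank test measures**

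With 47 and 48 patients (SAP 6.2) there are 47 × 48 = 2,256 between-arm pairs. U counts the pairs in which the patient from one arm has the larger value, and U/2,256 estimates the probability of that. No mean enters. The estimate that belongs to this test is the Hodges-Lehmann shift, the median of the 2,256 pairwise differences. Its interval comes from inverting the test under a shift model. If the arms differ by a pure shift, this equals the difference in means; otherwise it need not.

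Two constructed cases (10,000 trials each, 47 vs 48; Hodges-Lehmann shift computed on 2,000 of them) show how far apart the two can be:

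- Log-normal values, log-SD 1.0, log-shift 0.5. The true mean difference is e^0.5 × (e^0.5 − 1) = 1.649 × 0.649 = 1.07 (simulated 1.067). The average Hodges-Lehmann shift is 0.537.
- Equal means, different shapes (normal against centred log-normal). The mean difference averages 0.001 and the Hodges-Lehmann shift −0.416. Mann-Whitney is significant in 43.8% of trials, while the t interval excludes zero in 7.5%.

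**3. How often the verdicts differ**

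Discordance means that the t-based 95% CI for the mean difference excludes zero and Mann-Whitney gives p ≥ 0.05, or the reverse. Arm sizes come from the SAP. Every distribution is an assumption. In the log-normal rows the outcome is the change score, with a within-person correlation of 0.5 on the log scale. The range of log-SD 0.6-0.9 was run with 3,000 trials per setting.

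| Assumed data | No effect | Real shift |
|---|---|---|
| Normal, shift 0.3-0.575 SD | 2% | 6-7% |
| Log-normal change, log-SD 0.1-0.3, shifts giving roughly 50-83% power | about 2% | about 5-8% |
| Log-normal change, log-SD 0.6-0.9, log-shift 0.25-0.40 | about 4-5% | about 7-22% |

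Repeated runs move these rates by a percentage point or so. Under strong skew with a real shift the disagreement runs both ways: only the t interval is significant in about 3-5% of trials, and only the rank test in about 5-15%.

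**4. How strong the assumed skew is**

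The 95% range between patients spans a factor of e^(2 × 1.96 × log-SD). For log-SD 0.6 this is e^2.352, about 10-fold. For 0.9 it is e^3.528, about 34-fold. Such a spread is conceivable for viral load. Nothing in the documents shows it for the blood counts in 7.3, which include hemoglobin and HCT.

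**The case against.** The sentence in 7.3 may only be loose drafting: a mean change with a t-based between-arm interval, tested by whichever of the two tests applies. That is its most natural reading, and it confines the gap in 7.3 to the Mann-Whitney branch. It does not close the gap, because a mean-based interval still sits beside a rank p-value.

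Three stronger readings are tempting, and the documents do not support them:

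- A reader might infer that the trial would say whether the arms differ but not by how much. SAP 7 reports means and medians for each arm, and 7.1-7.3 compare mean changes, so a point difference is always available. What is missing is a between-arm estimate and interval that match the rank test.
- A reader might infer that the arms are to be compared through two separate per-arm intervals. SAP 7 lists those intervals as descriptive and assigns the comparison to a two-sample test.
- A reader might infer that the documents contain no estimation method. The baseline-adjusted regression in Protocol 7 would give a between-arm estimate with an interval. The SAP does not take it up, and the Protocol names a Wilcoxon test beside it, so it does not cure the SAP as written.

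It is also fair to say that two valid tests on the same data will sometimes fall on opposite sides of 0.05. The 6-7% seen with perfectly normal data is of that kind, so the lower end of the skewed range is partly ordinary borderline disagreement.

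**Conclusion.** The point holds as a reporting gap. SAP 7.3 pairs a mean change and its interval with a test that yields no such interval. SAP 7 extends the switch to every variable without naming an estimate, and 7.1 and 7.2 state no between-arm interval at all. This follows from the text and needs no simulation.

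The size is illustrative, because it rests on assumed distributions and a two-sided 5% level. Under low skew, discordance is close to what normal data give. The larger figures need strong skew, and it would be wrong to read 22% as a forecast for the tertiary blood counts. No sample size, power or error-rate figure in the plan changes. The severity is low: worth correcting, but not a threat to the validity of the trial.

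**What to change.** Add one rule to SAP 7, applying to 7.1, 7.2 and 7.3. For every continuous outcome, report the between-arm difference in change with its 95% CI. Where Mann-Whitney is the test, also report the Hodges-Lehmann shift with its 95% CI as the estimate that belongs to that p-value, and keep the mean difference as a descriptive figure. State that the Hodges-Lehmann interval assumes the arms differ by a shift. Reword 7.3 so that the interval is no longer attributed to Mann-Whitney U.

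An alternative is to bring the baseline-adjusted linear regression of Protocol 7 into the SAP. Estimate, interval and p-value would then come from one model, and the reported quantity would not vary by outcome with a Visit 1 normality check.

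The first option costs one sentence and one extra output column, and gives two summaries for each skewed outcome. Neither option changes data collection, sample size or conduct.
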